##### **3.2.1 The Endpoints are:**

- Retreatment through follow-up
- Procedural device-related serious adverse events at immediate post-procedure
- Ability to achieve adequate occlusion - based on investigator's adjudication of adequate occlusion given anatomical and other considerations immediate post-procedure
- Number of times re-access with guidewire was required due to catheter kickout

#### **3.3 Registry Population**

Patients enrolled in this registry must sign the informed consent form and be treated in accordance with the cleared indications outlined in the *Instructions for Use* for Smart, PC 400, and/or POD. Patients will be considered enrolled at the time of consent and procedure has begun with the intent of implanting coils.

Patients who fail to meet entry criteria pertaining to coil selection will be considered a screen fail and monitored through discharge for safety reasons.

### 3.3.1 Inclusion Criteria

Embolization of:

- Intracranial aneurysms
- Other neurovascular abnormalities such as arteriovenous malformations and arteriovenous fistulae

### 3.3.2 Exclusion Criteria

- Life expectancy less than one year
- Smart, PC 400, or POD account for less than 75% of total number of coils implanted
- Patient previously enrolled in the SMART Registry
- Participation in another clinical investigation that could confound the evaluation of the registry device

## 4. REGISTRY PROCEDURES

All registry procedures are to be conducted in accordance with the cleared indications outlined in the *Instructions for Use* for Smart, PC 400, and POD.

### SCHEDULE OF ASSESSMENTS

Assessment	Admission Evaluation	Immediate Post-Procedure	Discharge	One Year Follow-Up*
History	√			
Modified Rankin Scale**	√			√
Hunt and Hess +	√			
Aneurysm Occlusion		√		√
Procedural Data Points ++		√		
Adverse Events		√	√	√

\* Single follow-up visit to be conducted in accordance to the standard of care at the participating hospital. Period for which to capture follow-up visit is within one year  $\pm 6$  months

\*\* Only for patients in which mRS would be captured as standard of care

+ Required for patients with SAH only

++ Proportion of SMART coils implanted, target location access attempts, radiation exposure, coiling start/end time

## 5. INVESTIGATOR RESPONSIBILITIES

### 5.1 Institutional Review Board Approval / Ethics Committee Approval

Prior to enrolling patients into the registry, the investigator will ensure that proper Institutional Review Board (IRB) / Ethics Committee (EC) approval is obtained, in accordance with applicable local state and federal laws and regulations. The IRB/EC shall approve all registry documents, including the final protocol, amendments to the protocol, and the informed consent.

### 5.2 Informed Consent

The investigator is responsible for ensuring that a signed informed consent is obtained according to national and state requirements prior to inclusion of patients in the registry. For patients being treated in emergent cases (i.e. ruptured aneurysm) patients will be allowed to be enrolled if they sign consent no longer than 1 calendar day after the procedure, or if a legally authorized representative signs the informed consent on the patient's behalf.

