### 5.5.2 Adverse Event Reporting

Since this a post market registry, we will only be collecting Adverse Events (AEs) **related** to the procedure or device, unanticipated adverse device effects (UADE), and all Serious Adverse Events (SAEs) from the time of consent through registry exit. If an AE occurs that is not related to the procedure or device, it is not reportable under this Protocol.

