### 8.2 Patient Information and Consent

It is the responsibility of the investigator to give each patient full and adequate verbal and written information regarding the objective and procedure of the registry and the possible risks involved and to obtain signed informed consent from all patients prior to inclusion in the registry unless the patient's health condition does not allow informed consent, in which case the state and national procedures will be applied. For patients being treated in emergent cases (i.e. ruptured aneurysm), patients will be allowed to be enrolled if they sign consent no longer than 1 calendar day after the procedure or if a legally authorized representative signs the informed consent form on the patient's behalf. The original, signed consent is filed with the patient registry records, and a copy is provided to the patient or legally authorized representative.

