## 10 Safety Analysis

### 10.1 Primary Safety Analysis

The primary safety endpoint is the proportion of subjects who experience at least one procedural (within 24 hours of arterial puncture) device-related serious adverse event.

Frequency counts and percentages of subjects experiencing a procedural device-related serious adverse event will be provided. A 95% two-sided binomial proportion confidence interval will be reported using a normal approximation to the binomial.

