### Enrollment and Screening

| Subject               | Status   | Date of Consent | Reason Subject Not Enrolled  | Other, Specify | Not Consented and Not Enrolled Reason  | Other, Specify |
|-----------------------|--|-----------------|--|----------------|--|----------------|
| Subject not Consented | Consented and Enrolled
Consented and Not Enrolled
Not Consented and Not Enrolled | DDMONYYYY       | Less than 75% of total number of coils implanted are SMART, PC 400, or POD
Other, Specify | <Specify text> | Did not want to participate
Life expectancy less than 1 year
Subject already enrolled in SMART
Participating in another clinical investigation that could confound the evaluation of the registry device
Other | <Specify text> |

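### Late consent in emergent cases lets enrolment, and on a literal reading SAE collection, begin after the 24-hour primary safety window, and no planned analysis separates these patients

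*Protocol*

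**What the plan says.** **Consent.** Protocol 5.2 allows emergent patients (ruptured aneurysm) to enter after treatment: "patients will be allowed to be enrolled if they sign consent no longer than 1 calendar day after the procedure". The alternative route is signature by a representative with legal authority to act for them. Protocol 8.2 repeats the rule and refers to state and national procedures where the patient's condition rules out consent. Neither section sets a deadline for the representative or says whether a representative may sign for a patient who has died.

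**Enrolment and population.** Protocol 3.3: "Patients will be considered enrolled at the time of consent and procedure has begun with the intent of implanting coils". SAP 4.1 limits the ITT population to consented, enrolled subjects who meet the 75% coil rule, and classes patients without consent as screen failures.

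**Endpoint.** SAP 10.1 counts subjects with "at least one procedural (within 24 hours of arterial puncture) device-related serious adverse event".

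**Event collection.** Protocol 5.5.2 collects "all Serious Adverse Events (SAEs) from the time of consent through registry exit". SAP 10.2 uses the same starting point.

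**Screening record.** In the SAP Appendix (Enrollment and Screening table and listing), the reasons for patients neither consented nor enrolled are refusal ("Did not want to participate"), short life expectancy, prior enrolment, another study, and other. The listing adds a free-text field for the last. The date of consent is listed; the time is not.

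**The concern.** Consent timing can affect the primary safety rate in two ways.

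- **Selection.** When consent is sought after the procedure, site staff and family already know how it went. A patient who has died or is incapacitated cannot sign, and enters only if a representative does. If patients with an event are enrolled less often than patients without one, the rate among enrolled patients is too low.
- **Collection.** The endpoint clock starts at arterial puncture and the reporting clock starts at consent. For a late consenter, a literal reading leaves events in between unreportable, even though the patient enrols and counts in the denominator.

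Both act in the same direction, on one of the two primary endpoints, and in the emergent group. About 17 events are expected in 1,000 patients, so a few missing ones are noticeable. Information on patients who were never enrolled cannot be reliably rebuilt later.

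**Working it through.** **1. Timeline.** If one calendar day means the end of the day after the procedure, the deadline falls between 24 hours (procedure just before midnight) and 48 hours (just after midnight) after the procedure. The safety window closes 24 hours after arterial puncture, which is no later than 24 hours after the procedure. A patient's own consent may thus be signed after the whole safety window has passed.

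**2. The plan's own figure.** Inputs from Protocol 9.1 and SAP 2: rate 1.7%, n = 1,000, normal-approximation 95% interval.

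1.96 × √(0.017 × 0.983 / 1000) = 0.0080, giving 0.90% to 2.50%.

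The stated interval is 0.93% to 2.5%. The upper limit and the ±1% precision reproduce. The lower limit does not (Clopper-Pearson gives 0.99%, Wilson 1.06%). This small discrepancy does not affect the present point.

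**3. Selection, by assumption.** Let e be the share consenting late, r their true event rate, and m the share of their event patients never enrolled. Other patients have rate 1.7%, and all patients without an event are enrolled. The documents give none of e, r or m.

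True rate = (1 − e) × 0.017 + e × r

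Observed rate = [(1 − e) × 0.017 + e × r × (1 − m)] / [1 − e × r × m]

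With r = 1.7%, so that the true rate is 1.7%:

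| e | m = 25% | m = 50% | m = 75% |
|---|---|---|---|
| 20% | 1.62% | 1.53% | 1.45% |
| 40% | 1.53% | 1.36% | 1.20% |

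The two ends in full:
- e = 20%, m = 25%: (0.0136 + 0.00255) / 0.99915 = 1.62%, a relative loss of 5%.
- e = 40%, m = 75%: (0.0102 + 0.0017) / 0.9949 = 1.20%, a relative loss of 30%.

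**4. Collection gap.** If the patients enrol but their pre-consent events go unreported, the numerator is the same and the denominator stays whole. At the lower end the rate is 0.0119, or 1.19% instead of 1.20%. The two mechanisms are numerically almost interchangeable.

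**5. In patients.** With 17 events expected in 1,000, losing k event patients gives (17 − k)/(1000 − k):
- k = 3: 14/997 = 1.40%
- k = 5: 12/995 = 1.21%
- k = 8: 9/992 = 0.91%

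**6. What the planned outputs could show.**
- SAP 9 includes ruptured versus unruptured subgroups for the safety endpoint, but these contain enrolled patients only. The mock subgroup table has no safety row.
- SAP 12 limits its sensitivity analyses to the primary efficacy endpoint. The mock sensitivity table does carry a safety row, but only by follow-up completeness and imputation.
- The screening table counts patients without consent but has no row for death or incapacity.
- Protocol 3.3 monitors screen failures through discharge only when the failure concerns coil selection.

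None of these separates patients by consent timing.

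**The case against.** The strongest reply is that the protocol anticipates incapacity. A representative may sign with no stated deadline, and Protocol 8.2 adds state and national procedures. A reader might infer that emergent patients must survive the safety window in good condition to be enrolled; the documents do not support that. What remains is narrower: the route is optional, it is used when the outcome is known, and its application to a patient who has died is not addressed.

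A reader might also infer that the loss is invisible. It is not strictly so, because the listing's free-text field could hold death or incapacity before consent. But free text gives no planned count, and the table would show such patients only under other.

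Third, the size rests wholly on assumed inputs. This stands. A relative loss of 40% can be produced, but only with e = 40%, r = 3% and m = 75%, where the true rate is 2.22% and the observed rate 1.33%. It should not be attached to a true 1.7%.

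Fourth, the illustrated shift of 0.08 to 0.50 points lies within the ±0.80-point interval of a descriptive registry with no performance goal. That is correct, but the interval describes sampling error and does not reflect this bias.

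Fifth, the endpoint counts only device-related SAEs, so death or incapacity from the haemorrhage alone removes no endpoint event. This limits how large m is likely to be.

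Finally, patients consented before the procedure might be taken as an unselected comparison. They are not: late consent is confined to emergent cases, so that group would be largely elective, and its membership still depends on the 75% coil rule, known only after implantation.

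**Conclusion.** The point holds as a structural weakness. The texts allow consent after the primary safety window, make ITT membership depend on consent, start SAE collection at consent, and plan no analysis by consent timing. The likely direction is a rate that is too low. That the rate will in fact be biased, and by how much, cannot be shown from the documents.

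Under the stated assumptions (20% to 40% late consent, equal event rates, 25% to 75% of late-consent event patients not enrolled) a true 1.7% would be seen as 1.62% down to 1.20%. If representatives sign for nearly all affected patients and sites already report events back to puncture, the effect would be close to nil. The plan should be changed because, as written, the final data could not distinguish these situations. The mismatch between the reporting and endpoint clocks is the firmest part, since it rests on wording alone.

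**What to change.** 1. **Record consent timing and signer.** Add an eCRF item for consent before or after the procedure, and whether patient or representative signed. The listed date cannot order same-day cases.
2. **Add a sensitivity analysis to SAP 10.1.** Report the primary safety endpoint by consent timing within rupture status. Label it a sensitivity analysis, not an unselected estimate.
3. **Add a screening reason.** Include treated, died or incapacitated before consent among the not-enrolled reasons in the screening log, table and listing. With x events in n enrolled patients and k such patients, the rate can be bounded between x/(n + k) and (x + k)/(n + k), treating all k as otherwise eligible. For example, x = 12, n = 995, k = 5 gives 1.20% to 1.70%.
4. **Align the clocks.** State in Protocol 5.5.2 and SAP 10.2 that for late consenters SAEs are collected back to arterial puncture, matching SAP 10.1. Without this, the split in item 2 would compare groups with different collection windows.

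The cost is one small addition to the eCRF, one screening category, one table and a wording change. The strata will be thin: 200 to 400 late consenters at 1.7% means 3.4 to 6.8 expected events, so intervals will be wide and should be exact rather than normal-approximation. The bound in item 3 covers only patients who are logged, and not those able to consent who refuse after an event.

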### 5.3 Adherence to Protocol/Amendments and Applicable Law

The investigator is responsible for ensuring that the registry is conducted according to this protocol and in accordance with the relevant aspects of EN ISO 14155:2011, Declaration of Helsinki, along with any conditions imposed by the reviewing Institutional Review Board (IRB) or Ethics Committee (EC), and all other applicable regulations. The investigator shall approve and adhere to this protocol and any amendments that arise during the course of the registry.

It is the investigator's responsibility to ensure that the staff assisting with the registry have the appropriate qualifications, are fully instructed on the registry procedures, and will respect the confidentiality statement.

### 5.4 Case Report Form Completion

The investigator and registry staff shall complete the electronic case report forms (eCRFs) associated with this registry. Patient numbers shall be used to identify individual patients in this registry. The eCRFs should be a complete and accurate record of patient data collected during the registry. It is the investigator's responsibility to ensure the quality of the data collected and recorded.

### 5.5 Reports

The investigator will be responsible for the following reports:

### 5.5.1 Protocol Deviation

Any deviations from the protocol identified during monitoring or through other means should be clearly documented. These include but are not limited to:

- Subject does not meet inclusion/exclusion criteria
- Incomplete or missing data
- Failure to sign informed consent
- Improperly signed or incomplete informed consent
- Delayed reporting of serious, device related, or unexpected adverse events
- Out of window visits or assessments

### 5.5.2 Adverse Event Reporting

Since this a post market registry, we will only be collecting Adverse Events (AEs) **related** to the procedure or device, unanticipated adverse device effects (UADE), and all Serious Adverse Events (SAEs) from the time of consent through registry exit. If an AE occurs that is not related to the procedure or device, it is not reportable under this Protocol.

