## 1 Overview

SMART is a multicenter, single-arm prospective registry. Its primary objective is to acquire postmarket data on the use of the Penumbra SMART COIL® System (Smart) in the treatment of intracranial aneurysms and other malformations.

Approximately 1,000 subjects with intracranial aneurysms or other malformations treated by Smart will be enrolled across up to 100 sites. All subjects will be allocated to treatment with at least 75% Smart, Penumbra Coil 400™ (PC 400), or Penumbra Occlusion Device (POD®) coils as defined by the number of coils implanted.

The primary efficacy endpoint is the rate of retreatment through one year  $\pm$  6 months follow-up. The primary safety endpoint is the rate of procedural (within 24 hours of arterial puncture) device-related serious adverse events.

The secondary efficacy endpoints for the registry are the ability to achieve adequate occlusion at immediate post-procedure (Class I or II Raymond-Roy Occlusion Classification for aneurysms) and the number of times re-access with guidewire was required due to catheter kickout while using SMART/POD/PC 400.

This Statistical Analysis Plan (SAP) elaborates on statistical methods outlined in the registry protocol and presents analysis conventions. The SAP will be signed off before database lock.

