## 4 Analysis Populations

### 4.1 Definitions

The ITT population will consist of all subjects who sign the informed consent and are enrolled in the registry with Smart, PC 400, or POD accounting for 75% or more of the total number of coils implanted. The ITT population will include only the first lesion treated for each subject. Summary statistics will be developed separately for additional lesions.

The PP population will be constructed by excluding subjects who have major protocol violations that impact endpoint evaluations. Subjects will be classified as screen failures if they are not consented or are consented and not enrolled due to failure to implant at least 75% Smart, PC 400, or POD coils or other reasons.

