### 10.2 Analysis of Adverse Events

Only adverse events that are related to the procedure or device, unanticipated adverse device effects (UADE), and all serious adverse events (SAE) from consent through registry exit are reportable under the SMART protocol. Reported adverse event data will be presented for each subject, including actions taken, causality (if appropriate), outcome, seriousness, severity, and start and end dates. The onset of adverse events will also be shown relative (in number of days) to the day of treatment. All adverse events will be reported based on the assessment from the clinical study sites.

Rates of device or procedure related adverse events and serious adverse events will be calculated, broken down by category. These reports will count only the most severe adverse event for each subject and only those categories with at least 3% subjects included. Tabulations and descriptive statistics will be produced, including an analysis by time period: (1) intraprocedural or within 24 hours of procedure and (2) after 24 hours post-procedure.

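### Event collection is stated to start at consent, but emergent patients may consent after the 24-hour primary safety window has closed (minor)

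*Protocol*

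**What the plan says.** **Start of collection.** Protocol 5.5.2 says that only three kinds of event are collected: AEs related to the procedure or device, UADEs, and "all Serious Adverse Events (SAEs) from the time of consent through registry exit". SAP 10.2 gives the same list and ends it in the same way: "all serious adverse events (SAE) from consent through registry exit are reportable under the SMART protocol". It restates the protocol rule and is not separate support for it.

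**Timing of consent.** Protocol 5.2 says of emergent cases, with ruptured aneurysm as the example, that "patients will be allowed to be enrolled if they sign consent no longer than 1 calendar day after the procedure". Protocol 8.2 repeats this and likewise gives the alternative of signature by a representative: "if they sign consent no longer than 1 calendar day after the procedure or if a legally authorized representative signs".

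**Endpoint window.** SAP 1 states: "The primary safety endpoint is the rate of procedural (within 24 hours of arterial puncture) device-related serious adverse events". SAP 10.1 counts subjects with "at least one procedural (within 24 hours of arterial puncture) device-related serious adverse event". Neither section sets a condition on when consent was given.

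**What is not said.** No section states whether the consent start applies to all three kinds of event or only to the last. None states that events before a late consent are to be entered retrospectively.

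**The concern.** The endpoint clock starts at arterial puncture. The collection clock, as worded, starts at consent. For a patient who consents before the procedure the difference does not matter. For an emergent patient who signs afterwards, part or all of the 24-hour window can lie before collection starts.

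The phrase in Protocol 5.5.2 gives both a start and an end, and it closes a sentence that says what will be collected. Reading it as covering the whole list is natural; otherwise that section would give no collection period for related AEs or UADEs. Protocol 3.3 also makes enrollment depend on consent, so a site could reasonably treat an earlier event as outside the registry.

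Any loss runs in one direction: it lowers the primary safety rate. It would fall mainly on ruptured aneurysms, because late consent is reserved for emergent cases, and rupture status is a planned subgroup for the safety endpoint (SAP 9). Events that were never collected cannot be recovered in the analysis. With up to 100 centers, different readings would also make ascertainment uneven between sites.

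**Working it through.** **1. The plan's own figure.** Inputs: rate 1.7% and n of about 1,000 (Protocol 9.1, SAP 2); normal-approximation 95% interval (SAP 2).

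Half-width = 1.96 × √(0.017 × 0.983 / 1000) = 0.00801, or 0.80 points. The interval is 0.90% to 2.50%. The plan states 0.93% to 2.5%. The upper limit and the ±1% precision reproduce. The lower limit fits an unrounded rate near 1.735%, which gives 0.93% to 2.54%. Nothing below depends on this difference. The expected count is 0.017 × 1000 = 17 subjects.

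**2. Latest permitted consent, in hours after puncture.**
- Counted by date (to the end of the next day), for a puncture at clock hour h and a procedure that ends the same day: 48 − h. For h = 8, 12 and 18 this is 40, 36 and 30 hours.
- Counted as 24 hours after the procedure: 24 plus the time from puncture to the end of the procedure.

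Both exceed 24 hours, so a permitted consent can follow the whole window. This is the deadline. Patients may sign earlier and lose only part of the window, or none of it.

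**3. Size if the consent start is applied to the whole list.** The documents give none of the three drivers, so all are assumptions:
- p: share of sites that apply the consent start to every item
- s: share of subjects who consent late
- f: among late consenters with an endpoint event, the share whose qualifying events all precede consent

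At equal risk, shift in points = p × s × f × 1.7.

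| p | s | f | Shift (points) | Observed rate | Subjects missed, of 17 |
|---|---|---|---|---|---|
| 0 | any | any | 0 | 1.70% | 0 |
| 0.5 | 5% | 0.5 | 0.021 | 1.68% | 0.21 |
| 0.5 | 10% | 1 | 0.085 | 1.62% | 0.85 |
| 1 | 5% | 0.5 | 0.043 | 1.66% | 0.43 |
| 1 | 10% | 0.5 | 0.085 | 1.62% | 0.85 |
| 1 | 10% | 1 | 0.170 | 1.53% | 1.7 |

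The largest shift here is 0.170 / 0.801 = 21% of the half-width. At equal risk with p = f = 1, the shift equals the half-width only when s = 0.801 / 1.7 = 47%.

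**4. Unequal risk.** Suppose late consenters have twice the risk of the others, with p = f = 1 and the overall true rate held at 1.7%. The observed rate is then 1.7 × (1 − s) / (1 + s).
- s = 10%: 1.7 × 0.9 / 1.1 = 1.39%, a shift of 0.31 points.
- s = 30%: 1.7 × 0.7 / 1.3 = 0.92%, with an upper limit of 1.51%, below the true 1.7%.

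The last case needs a large late share, doubled risk, every event lost and every site on the same reading. The documents support none of these, so it marks an extreme and is not an expectation.

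**The case against.** The strongest reply is that the consent phrase follows directly on the all-cause SAE item and may limit only that item. A device-related SAE is then reportable under the first item, with no consent limit. Other text points the same way:
- The next sentence of Protocol 5.5.2 excludes by relatedness, not by date: "If an AE occurs that is not related to the procedure or device, it is not reportable under this Protocol".
- Protocol 5.5.2.3 requires related events to be reported once they are known.
- Protocol 3.2.1 places this endpoint at immediate post-procedure, and the schedule in Protocol 4 records adverse events there with no exception for late consenters.
- SAP 10.2 dates onset from the day of treatment and tabulates a period that includes the procedure itself.
- Protocol 6.3 brings in events found during monitoring.

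A representative may also sign before the procedure, which closes the gap. Instructions could exist in the eCRF guidance or site training, which are not among the documents.

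Most of this stands. It shows that the sponsor probably means these events to count, and under that reading the primary endpoint is unaffected. What it lacks is a rule: none of these sections deals with consent given after the procedure. The reporting clock in Protocol 5.5.2.3 makes no provision for an event already known before consent.

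A reader might infer two stronger things. The first is that the plan as written will miss primary safety events. The sections above do not support that; a loss occurs only where a site applies the consent start to the whole list. The second is that SAP 4.1 makes such subjects count as event-free. It says only who belongs: "The ITT population will consist of all subjects who sign the informed consent and are enrolled in the registry". It is silent on event status, SAP 8.1 assigns the ITT and PP populations to the efficacy endpoints, and SAP 10.1 names no population.

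**Conclusion.** The stated start of collection and the primary safety window do not match for emergent patients who consent after treatment, and the documents do not say which governs. Applied to the whole list, the consent start undercounts the primary safety endpoint; limited to all-cause SAEs, it does not.

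The size cannot be set from the documents. With up to 10% late consent and equal risk (both assumptions), the shift is 0 to about 0.17 points, or 0 to 1.7 of 17 expected subjects, against a half-width of 0.80 points. Higher risk in late consenters would enlarge it. The registry is descriptive, with no performance goal or test on this rate, so what is at stake is the accuracy and uniformity of one reported figure. The point is minor, but worth settling because the bias can only run downward and the remedy is cheap.

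**What to change.** State in SAP 10.1 and 10.2 and in the eCRF instructions, and in Protocol 5.5.2 at its next amendment, that for every enrolled subject device- or procedure-related events are collected from arterial puncture of the index procedure, or from consent if that is earlier, through registry exit. Add that events before a late consent are entered retrospectively from source. The start of all-cause SAE collection need not change, because the primary endpoint is limited to device-related events.

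The cost is low. The procedural data in the Protocol 4 schedule already predate a late consent and have to come from source, and Protocol 6.4.2 names the operative report and discharge summary among the records that monitors may request. No extra analysis or sample size is needed. There are two downsides. The reported rate may be slightly higher. The protocol wording needs IRB/EC approval (Protocol 5.1) across up to 100 centers, which is why it can wait for the next amendment while the SAP and eCRF text is settled first.
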